6.6 Prior and Concomitant Medications

Commencing with signing the ICF, all medications (both prescription and over-the-counter), vitamin and/or mineral supplements, and/or herbs the subjects take through the End of Study (EOS) (or ET) will be documented on the concomitant medication electronic case report forms (eCRFs). Documentation will include start and stop date, dose and route of administration, dosing frequency, and indication.

6.6.1 Prohibited and Restricted Medications

Subjects must not take any medication for chronic pain during the study (through the end of the Treatment Period) that was not provided by the sponsor (including rescue medication) and should be reminded of such at each study visit. Use of moderate to strong cytochrome P450 3A4 (CYP3A4) inhibitors and inducers is prohibited throughout the study.

Subjects who have been taking opioid-containing medications prior to study start (no less than 10 mg MSE/day and no more than 60 mg MSE/day) will be eligible to participate. However, the opioid must be tapered to no more than 30 mg MSE/day for at least 3 days prior to Visit 3, then completely discontinued prior to starting NKTR-181. Concomitant use of opioids with NKTR-181 is prohibited. Use of these medications will be documented on the concomitant medication eCRFs and will include start and stop date, dose and route of administration, dosing frequency, and indication.

6.6.2 Permitted Medications

Subjects may use the following medications while participating in this study:

- Medications for stable diseases (e.g., metformin for diabetes. Note that NKTR-181 may increase the exposure of metformin; serum glucose levels should be monitored closely)
- Hypnotics or barbiturates if stable for at least 21 days prior to screening
- Adjuvant analgesics (e.g., antiepileptics, muscle relaxants for muscle spasms, triptans for migraine [no opioid treatment for migraine will be allowed])
- Aspirin (≤ 325 mg) for cardiovascular prophylaxis
- Antiemetics for nausea and vomiting
- Psyllium husks, stool softeners, laxatives, enemas, and peripherally acting mu-opioid receptor antagonists (PAMORAs; e.g., MOVANTIKTM) for opioid-induced constipation
- Medications to treat AEs or exacerbation of existing medical conditions
- Hormonal birth control
- Injected, topical, optical, or inhaled/nasal corticosteroids

Allowed rescue medication is described in Section [6.4](#)

6.7 Assigning Subject Numbers

Each subject will be assigned a unique subject number at Visit 1 of the Screening Period after signing the ICF. This unique subject number will be used on all subjects' study information. Subject numbers assigned to those subjects who fail the Screening Period or who withdraw from the Treatment Period will not be reassigned. Rollover Subjects will retain their subject ID from Study 14-181-07 or Study 14-181-12. For De Novo Subject, the first 4 digits will be the unique

site number (XXXX) followed by another 4-digit subject ID (YYYY), which together will be the unique subject number (e.g., XXXX-YYYY). The second set of 4 digits (YYYY) will be sequential within sites, starting with 8001 (indicating that the subject is a De Novo Subject).

7.0 INVESTIGATIONAL PRODUCT(S)/STUDY DRUGS

7.1 Description and Formulation

7.1.1 Study Drug Description

NKTR-181 (referred to as the study drug) will be administered orally in tablet form. Study drug tablets are white-coated and are available in dosing strengths of 100 mg and 200 mg.

NKTR-181 dosage strengths to be evaluated are 100 mg, 200 mg, 300 mg, and 400 mg BID. Each dose of study drug will consist of matching tablets as follows:

- 100-mg dose = 1 × 100-mg NKTR-181 tablet
- 200-mg dose = 1 × 200-mg NKTR-181 tablet
- 300-mg dose = 1 x 200-mg NKTR-181 tablet + 1 x 100-mg NKTR-181 tablet
- 400-mg dose = 2 × 200-mg NKTR-181 tablets
- 500-mg dose = 2 × 200-mg tablets + 1 × 100-mg NKTR-181 tablet
- 600-mg dose = 3 × 200-mg NKTR-181 tablets

7.1.2 Rescue Medication

For subjects who are experiencing breakthrough pain, the sponsor will provide aspirin, acetaminophen, ibuprofen, and naproxen for use as rescue medication. Aspirin will be provided in 325-mg tablets for oral use. Acetaminophen will be provided in 500-mg tablets for oral use. Ibuprofen will be provided in 200-mg tablets for oral use. Naproxen will be provided in 220-mg tablets for oral use, as directed on label.

7.2 Study Drug Packaging and Labeling

NKTR-181 tablets are packaged in cold-sealed blister packs that are inserted into wallets and contained in a metalized pouch with a desiccant. Sufficient drug to provide up to 10 days of dosing will be packaged in a wallet. Pouches and wallets are minimally labeled to be compliant with US Food and Drug Administration (FDA).

7.3 Study Drug Storage

Study drug must be stored at controlled room temperature in a secure area. NKTR-181 is designated a Schedule II drug and must be handled, stored, and accounted for in accordance with all federal, state, and local regulations for a Schedule II drug.

7.4 Accountability and Reconciliation

The Investigator is responsible for ensuring accountability of all study medications supplied and appropriate storage and allocation of these supplies.

The Investigator is responsible for ensuring that all study drugs and rescue medications received at the site are inventoried and accountability performed and that dispensed study drug is recorded in both the eCRF and the study drug accountability logs. The Investigator or designee will verify study drug accountability with subjects during site visits. Any discrepancies should be investigated. The Investigator will not supply study drug or rescue medication to any person except those who are subjects in this study and will not dispense study drug or rescue medication from any site other than those listed on Form FDA 1572. Study medication and rescue medication may not be relabeled or reassigned for use by other subjects.

All unused or damaged study drug or rescue medication will be returned and unit counts will be performed whenever medication is returned. The site must account for all medication received. The site will retain and store all study drug and rescue medication until inventoried by the study monitor. All returned, unused, and damaged study drug and rescue medication will be returned to the sponsor or designee for destruction.

8.0 PHARMACOKINETIC MEASUREMENTS

This study will investigate the PK of NKTR-181 in patients with chronic low back pain or chronic noncancer pain.

8.1 Pharmacokinetic Blood Sample Collection

Blood samples for PK analysis will be collected from all subjects according to the Schedule of Assessments (Section 1.2). Each participating site will be provided instructions for specimen collection, processing, storage, packaging, and shipment. **The first PK blood sample must be collected from all subjects prior to receiving the first dose of study drug (Visit 3).**

In a PK substudy of approximately 100 subjects at selected sites, serial blood samples will also be collected during a complete 12-hour dosing interval as shown in [Table 2](#).

Table 2: Pharmacokinetic Sample Collection Times in the PK Substudy

Time (hours)	Event ^a	Sample Name	Actual Time (example)
Predose	Cryovial Preparation		Approximately 15 - 30 min
Predose	Sample collection	Predose	Within 15 mins prior to dosing
0:00	NKTR-181 dosing		9:00 AM
0:30	Sample collection	0.5 hour postdose	9:30 AM
1:00	Sample collection	1.0 hour postdose	10:00 AM
2:00	Sample collection	2.0 hours postdose	11:00 AM
3:00	Sample collection	3.0 hours postdose	12:00 PM
4:00	Sample collection	4.0 hours postdose	1:00 PM
5:00	Sample collection	5.0 hours postdose	2:00 PM
6:00	Sample collection	6.0 hours postdose	3:00 PM
8:00	Sample collection	8.0 hours postdose	5:00 PM
12:00	Sample collection	12.0 hours postdose	9:00 PM

^a Cryovials for PK sample collection must be prepared in advance of the first sample collection time on the day of collection and must undergo processing steps following sample collection according to the instructions provided in the Laboratory Manual.

8.2 Pharmacokinetic Analysis of Samples

Plasma concentrations of NKTR-181 and selected metabolites will be tabulated by time and subject and inspected for relationship to dose during the treatment phase. These data will be pooled with those from other studies during Population PK analyses and investigation of exposure-response relationships for efficacy and safety that will be specified in a population PK Analysis Plan.

9.0 EFFICACY ASSESSMENTS

9.1 Modified Brief Pain Inventory-Short Form (mBPI-SF)

The mBPI-SF ([Mendoza, 2006](#)) was developed to provide information on pain intensity and the degree to which pain interferes with patient functioning. Using a 0 to 10 numerical rating scale (NRS), subjects rate their pain at the time of responding to the questionnaire (Pain Now), and also at its worst, least, and average over the previous 24 hours. With 0 being "no interference" and 10 being "interferes completely," the mBPI-SF asks for ratings of the degree to which pain interferes with mood, walking and other physical activity, work, social activity, relations with others, and sleep.

10.0 ASSESSMENT OF SAFETY

10.1 Adverse Events and Serious Adverse Events

10.1.1 Adverse Events Definition and Assessment

An AE is defined as any untoward medical occurrence in a subject who is administered a medicinal product and that does not necessarily have a causal relationship with this treatment.

An AE can therefore be any unfavorable and unintended sign, symptom, or disease temporally associated with the use of a medicinal product, regardless of whether or not it is considered related to the medicinal product. An AE can also arise from any use of the drug and from any route of administration, formulation, or dose. This definition includes intercurrent illnesses or injuries, and exacerbation of preexisting conditions as well as events attributed to protocol-mandated procedures. Clinical laboratory abnormalities will only be reported as AEs if they are deemed clinically significant by the Investigator and/or are associated with signs and symptoms, require treatment, or require follow-up.

An AE does not include the following:

- A medical or surgical procedure (e.g., surgery, endoscopy, tooth extraction, or transfusion); an AE is the underlying condition that leads to the procedure.
- Preexisting diseases or conditions present or detected before the start of study drug administration that do not worsen or increase in severity or frequency after the administration of study drug.
- Situations where an untoward medical occurrence has not occurred (e.g., hospitalization for elective surgery for a condition that has not worsened on study, social and/or convenience admissions to grant families a respite in caring for a subject).
- Adverse events that start in Study 14-181-07 and Study 14-181-12 and are ongoing during this study will continue to be followed for Rollover Subjects.

10.1.2 Monitoring Adverse Events

All AEs will be assessed by the Investigator and recorded on the eCRF, including but not limited to the following: the event term, the date of onset and resolution, seriousness, severity, relationship to study drug, outcome, treatment of the event, and action taken with the study drug. Adverse events will be reported starting immediately after the subject has provided written informed consent through the EOS Visit (Visit 24/EOS).

Any AE attributed to a protocol-mandated procedure occurring after the subject has provided informed consent but prior to the first dose of study drug should be recorded on the eCRF as an AE.

Adverse events that are not attributed to protocol-mandated procedures occurring after signing of the informed consent but before the first dose of study drug will be reported as medical history.

Example 1:

Thrombophlebitis associated with a blood draw for assessments required prior to dosing per protocol is an event that is related to protocol-mandated procedures. In this scenario, the event of “thrombophlebitis” will be captured as an AE on the eCRF page, and it will be documented as being “unrelated” to study drug as applicable.

Example 2:

An ankle sprain following an unexpected fall from a flight of stairs while at home, after the subject has provided informed consent, but before the first dose of study drug, is clearly unrelated to any protocol-mandated procedures and would therefore be captured as medical history in the medical history section of the eCRF.

10.1.3 Grading of Adverse Events

The severity of an event and the seriousness are not to be considered synonymous. The severity is grading the intensity of an event. The seriousness of an event is based on the subject/event outcome (Section 10.1.6). All AEs will be assessed for severity by the Investigator using the following criteria:

- Mild: The event results in mild or transient discomfort, not requiring or needing only minimal intervention or treatment; does not limit or interfere with daily activities (e.g., insomnia, mild headache);
- Moderate: The event is sufficiently discomforting so as to limit or interfere with daily activities; may require interventional treatment (e.g., fever requiring antipyretic medication); and
- Severe: The event results in significant symptoms that prevent normal daily activities; may require hospitalization or invasive intervention.

10.1.4 Causality Relationship of Adverse Events

The relationship of each AE to the study drug will be evaluated by the Investigator using the following definitions:

- Not related: The AE is clearly not related to the study drug(s). The AE can be explained to be likely related to other factors such as concomitant medications or the subject's clinical state;
- Unlikely related: The AE is doubtfully related to the study drug(s). The current knowledge or information about the AE indicates that a relationship to the study drug is unlikely;
- Possibly related: The AE may be related to the study drug(s). A plausible temporal sequence exists between the time of administration of the study drug and the development of the AE, and it follows a known response pattern to the study drug. The AE is unlikely explained by the known characteristics of the subject's clinical state or other concomitant therapies or interventions administered to the subject; and
- Related: The AE is clearly related to the study drug(s). A plausible temporal sequence exists between the time of administration of the study drug and the development of the AE, and it follows a known response pattern to the study drug. The AE cannot be reasonably explained by the known characteristics of the subject's clinical state or other concomitant therapies or interventions administered to the subject. Additionally, the occurrence of this AE can be confirmed with a positive re-challenge test or supporting laboratory data.

The causality criteria of "related" and "possibly related" will be considered related to the study drug as applicable for regulatory reporting requirements.

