10.1.8 Serious Adverse Event Follow-up

All SAEs will be followed until resolution, stabilization of condition, return to baseline, or until follow-up is no longer possible.

Any SAE occurring after the end of the study for a subject but within 14 days of the subject’s last dose of study drug will be captured only if assessed by the Investigator as related to study drug.

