10.1.9 Expedited Reporting of Serious Adverse Events

A suspected unexpected serious adverse reaction (SUSAR) is an SAE that is considered “unexpected” and is assessed by the Investigator or the sponsor as related to the study drug. All SAEs deemed related to the study drug and not expected based on the most current NKTR-181 Investigator’s Brochure are subject to expedited reporting to the applicable regulatory authorities by the sponsor. Therefore, the Investigator or site personnel must report all SAEs to Nektar Therapeutics Drug Safety or its designee within **24 hours** of first becoming aware of the event.

Fatal or life-threatening SUSARs will be reported to the regulatory authorities by the sponsor as soon as possible but no later than 7 calendar days after the sponsor or its designee has first knowledge of the minimum criteria for expedited reporting, with a full written report within 8 calendar days later. Nonfatal or nonlife-threatening SUSARs will be reported to the regulatory authorities, IRBs, and Investigators as soon as possible but no later than 15 calendar days after the sponsor or its designee has first knowledge of the SUSAR.

Reporting of SUSARs to all applicable regulatory authorities will be made by Nektar Therapeutics Drug Safety or its designee as per local country and regional regulations.

Notification of SUSARs to the central IRBs will be made by Nektar Therapeutics Clinical Operations or its designee in accordance with the SOPs and policies of the IRBs. Reporting to local IRBs will be made by the applicable study site personnel per their institutional guidelines. Adequate documentation must be provided to Nektar Therapeutics Clinical Operations or its designee showing that the local IRB was properly notified.

Reporting of SUSARs to all participating clinical Investigators will be done by Nektar Therapeutics Clinical Operations or its designee per local regulations.

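### Read strictly, protocol 10.1.4 has no 'related' category for a well-timed reaction outside the drug's known response pattern, which weakens but does not block SUSAR identification

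*Protocol*

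**What the plan says.** Protocol 10.1.4 tells the Investigator to place each AE in one of four categories: 'Not related', 'Unlikely related', 'Possibly related' or 'Related'. The last two each require a plausible time course "and it follows a known response pattern to the study drug", and each also asks that other explanations be unlikely or not reasonable. Only these two "will be considered related to the study drug as applicable for regulatory reporting requirements".

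Three other parts of the plan use the rating:

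- **Expedited reporting (10.1.9).** A SUSAR is an SAE that is unexpected "and is assessed by the Investigator or the sponsor as related to the study drug". Expectedness is judged against the Investigator's Brochure: the section sends to the authorities "All SAEs deemed related to the study drug and not expected based on the most current NKTR-181" Brochure.
- **SAEs after the subject's study has ended (10.1.7, 10.1.8).** Within 14 days of the last dose, such an SAE "will be captured only if assessed by the Investigator as related to study drug".
- **AE tables (protocol 11.9.3, SAP 8.7.1).** AEs are tabulated by relationship to study drug, using the Investigator's rating.

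**The concern.** Causality and expectedness are separate questions. Causality asks whether the drug may have caused the event; expectedness asks whether that effect was already documented. Requiring a known response pattern before an event can be called even possibly related brings prior knowledge into the causality judgement. The events least likely to meet the condition are those with no precedent, and SUSAR reporting exists to find them.

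The setting makes this matter more. The primary objective is long-term safety, the drug is a new molecular entity, and treatment runs for up to 52 weeks at up to 600 mg BID. The prior experience cited in protocol 2.3 is three Phase 1 studies, one Phase 2 study of about 200 subjects, and over 330 subjects titrated to 400 mg in a study still under way. The known pattern is therefore likely to be incomplete. There is no concurrent control arm against which an under-attributed event could be noticed.

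**Working it through.** No figure in the plan is at stake, so the check sets the definitions side by side and then sizes the one part that can be sized, the post-study window.

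**Step 1. The conditions of the four categories.** Take a test event with good timing, no likely alternative cause, and no precedent with this drug or its known pharmacology.

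| Category (10.1.4) | Deciding condition | Does the test event meet it? |
|---|---|---|
| Related | "it follows a known response pattern to the study drug. The AE cannot be reasonably explained by the known characteristics", with rechallenge or laboratory support in addition | No: there is no known pattern |
| Possibly related | "it follows a known response pattern to the study drug. The AE is unlikely explained by the known characteristics" | No, for the same reason; timing and alternative cause are satisfied |
| Unlikely related | "The current knowledge or information about the AE indicates that a relationship to the study drug is unlikely" | No: knowledge is silent, not contrary |
| Not related | Clearly unrelated, with other factors as the likely explanation | No |

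The known-pattern clause is joined by 'and' in both upper categories, and nothing elsewhere in the protocol or SAP relaxes it. Read strictly, the test event fits none of the four categories. If it is put into either lower one, it counts as not related for reporting.

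**Step 2. SUSAR identification.** 10.1.9 needs unexpectedness plus relatedness as judged by either of two parties.

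- *Investigator's route:* impaired for the test event, by Step 1.
- *Sponsor's route:* open. Under 10.1.7 all on-study SAEs go to the sponsor within 24 hours whatever their causality. The definitions in 10.1.4 are addressed to the Investigator, and the documents state no separate causality criteria for the sponsor.

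**Step 3. AE tables.** Under protocol 11.9.3 and SAP 8.7.1 the test event may sit under a lower causality rating. The summaries of TEAEs, SAEs, deaths and AEs leading to withdrawal, and the event rates per 100 patient-years, do not depend on the rating, so it stays in those.

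**Step 4. Post-study SAEs.** The exposed window is 14 days after last dose minus the day of the final visit. I assume that follow-up visits are timed from the last dose, as the protocol synopsis describes the follow-up period.

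- Visit 24 at its earliest allowed day: 14 − 2 = day 12, so the window is 14 − 12 = 2 days.
- Visit 24 on day 14 or later: 14 − 14 = 0 days.
- Last attended visit is Visit 23 at 72 hours (day 3): 14 − 3 = 11 days.
- No visit after the last dose: up to 14 days.

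Within this window the sponsor's route gives little protection, because an SAE not rated related by the Investigator need not be sent to the sponsor. Fatal events are an exception in principle, since 10.1.6 requires all of them to be reported regardless of causality.

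**The case against.** The strongest reply is that the practical damage is small, and most of that reply stands.

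- **Forced downgrading.** A reader might infer that an unexpected event must be rated unlikely or not related. The text does not say so. Those categories have their own conditions, which a novel, well-timed event does not meet, and 'Possibly related' opens by describing an event that may be related. An Investigator could sensibly choose it. The defect is a gap between categories.
- **Known is not the same as listed.** A reader might equate a known pattern with a Brochure listing and conclude that no SUSAR can arise from the Investigator's rating. 10.1.4 does not define the phrase, while 10.1.9 ties expectedness to the Brochure. A recognised opioid effect could be unlisted and still follow a known pattern. The conflict is confined to reactions new to the drug and its known pharmacology.
- **SUSAR reporting blocked.** The sponsor's independent assessment rules this out for on-study SAEs.
- **Loss from the safety tables.** Neither document specifies a table restricted to related TEAEs. SAP 8.7.1 presents AEs by the Investigator's rating, and causality is not part of the key AE endpoint, which is incidence, type, seriousness and severity.
- **Post-study events lost altogether.** For subjects who keep to the schedule the window is at most 2 days.

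What does not fall is the wording itself. The clause is a stated condition of both related categories, one of the two SUSAR routes depends on it, and so do the Investigator-causality tables and post-study capture.

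**Conclusion.** The point holds as a defect in the causality definitions with limited reach. For reactions outside the known response pattern, 10.1.4 read strictly offers no related category. As a result:

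- the Investigator's route to a SUSAR is weakened, with the sponsor's route intact for on-study SAEs;
- tables by Investigator causality may understate relatedness for such events, while the overall TEAE and SAE tables are unaffected;
- related-only capture of post-study SAEs is affected over 0 to 2 days for subjects who attend Visit 24 within its window, and over a longer period, up to 14 days, for those who leave follow-up early.

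The number of events cannot be given from the documents. The conclusion assumes that Investigators apply the definitions as written. If they give 'Possibly related' its looser, opening sense, the effect shrinks, but ratings will then vary between the roughly 100 sites according to how each reads the clause.

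**What to change.** 1. In protocol 10.1.4, make the known response pattern supportive and not required, at least for 'Possibly related'. For example: a plausible temporal sequence and a reasonable possibility that the drug contributed, whether or not the event follows a known pattern.
2. State in the same section that causality is judged independently of expectedness.
3. Ask Investigators to re-assess, under the revised definition, all SAEs already rated 'unlikely related'. A narrower query, limited to those rated so for want of a known pattern, is not workable: the AE fields listed in 10.1.2 include the relationship but not the reason for it.

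The cost is a short amendment or site letter and one round of SAE queries; design, visits and dosing are untouched. The downside is that more events will be rated related and reported, which is the safer direction of error in a long-term safety study. Re-assessment cannot recover post-study SAEs that were never captured.
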